## STATISTICAL DESIGN AND POWER

Descriptive statistics and exploratory graphing will be generated for all variables of interest measured at all time points (i.e., baseline, mid-treatment, post-treatment, 3-month follow-ups). Data summaries will be produced both for the combined sample, and separately by treatment condition. Variables will be transformed if necessary using Box-cox power transformation. Baseline characteristics will be compared between treatment conditions using ANOVA (or non-parametric Kruskal Wallis test, as appropriate) for continuous variables and a chi-square test for categorical variables. Key baseline variables that differ by condition will be considered for use as covariates in the analyses described below.

**Primary Aim 1.** To assess feasibility and acceptability, we will use the following benchmarks: (a) recruitment success: enrollment of 60 patients; (b) attrition: retention of >75% of patients through all assessments; (c) study retention: patients attend at least 90% of all treatment groups; (d) satisfaction: patients express high satisfaction with RRT based on feedback questionnaires.

**Primary Aim 2.** To evaluate the effect of each treatment condition on hypothesized targets, we will model the pattern of change in reward response to palatable food, reward response to day-to-day life activities, social isolation, and loneliness separately over time using multilevel models (PROC MIXED in SAS). The first level will model individual participant's score on the relevant target over time with baseline as time 0. At the second level, the individual intercept and slope will be entered as outcomes with treatment condition as a predictor. We will examine each treatment condition separately. The cross-level interaction between time and treatment condition will be used to determine the effect of treatment condition on the pattern of change in the hypothesized targets. Restricted maximum likelihood will be used to estimate model parameters and to test the significance of random effects. Both linear and higher-order time effects will be examined based on model selection criterion such as Akaike Information Criterion (AIC) and Bayesian Information Criterion (BIC). With the fitted multilevel model structure, statistical contrasts will be performed at mid-treatment, post-treatment, and 3-month follow-up.

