**Primary Aim 3.** Analyses will be conducted via linear mixed effects models for longitudinal data, which increase power by fully exploiting the strong correlation in treatment outcomes of interests (i.e., percent binge frequency reduction and percent change in EDE global eating pathology) across time. Patterned covariance matrices as implemented in (PROC MIXED in SAS) and will be used to evaluate between group differences for percent binge reduction and percent change in EDE global eating pathology across the study as a whole, and at each assessment post-baseline. Separate variance components will be used to capture therapist and participant-within-therapist variation. The within-subject covariance matrix will be assumed common across study arms, with an exponential variance function to deal with heteroscedasticity and a continuous-time AR(1) correlation matrix to accommodate residual autocorrelation over the unequal-size time intervals between follow-ups. Outcomes at all four time points will be estimated jointly for maximum statistical efficiency in the presence of intermittent missingness and loss to follow-up. The model will include random effects for subject and time (with higher-order effects if needed to capture nonlinear change), and fixed effects for treatment arm, time by treatment interaction, demographic information, and baseline values of binge frequency and global eating pathology. Time-specific covariate-adjusted contrasts will be used to compare outcome between groups.

**Secondary Aim 1.** We will use the same analytic approach described above for Primary Aim 3 but will test the impact of treatment condition on secondary outcomes including depression, substance abuse, and quality of

life.

**Attrition.** Patterns of missing data will be examined. Likelihood-based estimation methods and multiple imputation models will be used to handle missing data. In addition, we will use Hedeker and Gibbons' procedure to examine if dropouts influence the multilevel model results. If the missingness mechanism is related to the missing outcome itself, we will use sensitivity analyses to explore how robust our findings are with respect to a range of assumptions regarding missing data.

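### Primary Aim 3 models percent change from baseline at four time points, so a baseline row of zeros enters the model and can misstate standard errors or the treatment contrasts

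*SAP*

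**What the plan says.** SAP, Primary Aim 3, names its outcomes as "percent binge frequency reduction and percent change in EDE global eating pathology". It wants the arms compared "across the study as a whole, and at each assessment post-baseline", and adds: "Outcomes at all four time points will be estimated jointly for maximum statistical efficiency in the presence of intermittent missingness". The opening paragraph of the SAP lists the time points as "baseline, mid-treatment, post-treatment, 3-month follow-ups", and Protocol D.6 gives the same schedule. One of the four is therefore baseline, and only three come after it.

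All rows share one within-subject structure, "an exponential variance function to deal with heteroscedasticity and a continuous-time AR(1) correlation matrix", on top of random effects for participant and time. The SAP does not say whether time is categorical or continuous in the mean model; polynomial terms above linear are added only where needed.

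Three elements of the same paragraph fit post-baseline rows only: the visit-specific comparisons are post-baseline, the intervals are described as "unequal-size time intervals between follow-ups", and the fixed effects include "baseline values of binge frequency and global eating pathology". No sentence drops the baseline row or sets its variance to zero. Secondary Aim 1 takes over the same approach. Protocol D.6.2, by contrast, names the raw 28-day binge count and the raw EDE global score as the primary outcomes.

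**The concern.** Percent change at baseline is 0, without variance, for everyone in both arms. The planned covariance structure is smooth in time and shared by all visits. To get close to zero variance at week 0 it has to bend towards a variance that grows with time, and it then tends to be too small early and too large late. Standard errors at the real visits inherit that error. If time enters the mean as a line or a low-order curve, the zeros also anchor that curve and pull the contrasts away from the truth.

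Aim 3 supplies the preliminary efficacy estimates, and Protocol A.6 says the trial is meant to show whether a fully powered trial is worth doing. The SAP's fallback to effect sizes when underpowered does not protect against this: polynomial time can distort the effect sizes themselves, and their intervals use the affected standard errors.

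**Working it through.** **Plan's own figure.** The only related figure in the SAP is N = 154 (Power analyses). With d = 0.5 for a medium effect, two-sided 0.05, four equally spaced assessments and variance ratio 1, V = 1/5 = 0.2 and the noncentrality is (154/4) × 0.25 × 1/1.2 = 8.02. Power is 0.8035, so 154 reproduces. It is not in dispute.

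**Inputs from the documents.** 30 per arm (Protocol A.7); visits at baseline, after sessions 5 and 10, and at 3 months (D.6); weekly sessions (D.2); the covariance structure in Primary Aim 3.

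**Assumptions.** Weeks 0, 5, 10 and 23 (3 months taken as 13 weeks); SDs, correlations and effect shape; variance exponential in week; no therapist effect.

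**Step 1, simplest case.** With categorical visits and one pooled variance, a zero row among four gives model SE / true SE = sqrt(3/4) = 0.87. Type I error is 2 × (1 - Φ(1.96 × 0.87)), about 9%. This is simpler than the SAP's full model.

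**Step 2, the line by hand.** Take a true effect of 0, -20, -20, -20 at weeks 0, 5, 10, 23. The means are 9.5 weeks and -15 points, Sxx = 293 and Sxy = -190, so the least-squares slope is -0.648. The fitted effects at the three visits are -12.1, -15.3 and -23.8. A quadratic gives -15.2, -23.3 and -19.6.

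**Step 3, large samples, SAP covariance.** Minimise log|V| + tr(V⁻¹S) plus the mean-misfit term, where S has a zero baseline row and column. Model SE / true SE at mid / post / follow-up, equal SDs, correlation 0.3 to 0.8:

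- categorical: 0.62-0.72 / 0.77-0.86 / 1.16-1.39
- linear: 1.04-1.13 / 0.90-1.02 / 1.01-1.11
- quadratic: 0.69-0.84 / 0.65-0.77 / 1.18-1.42. A repeat fit at correlation 0.8 gave 0.97 at follow-up, so that last range is not settled.
- three post-baseline rows: 1.00 at each visit

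With unequal SDs of 30/40/45 (categorical visits, correlation 0.6), four rows gave 0.70 / 0.95 / 2.20 and three rows 1.08 / 0.91 / 1.04.

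**Step 4, simulation at 30 per arm.** EDE-like scores: baseline mean 3.0, SD 0.9 (redrawn if below 1.5); control means 2.1/1.8/1.8, SD 1.0; correlation 0.5 with baseline and 0.6 between follow-ups; clipped to 0-6. REML with a baseline covariate, t with 57 df, no missing data. There were 505 null trials and 400 with a true effect of -20.2 / -19.5 / -19.4 points. Order is mid / post / follow-up.

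| Time in mean model, rows | Type I error, % | Model SE / true SE | Mean estimate | 95% CI coverage, % |
|---|---|---|---|---|
| Categorical, four | 17.8 / 8.5 / 1.4 | 0.69 / 0.85 / 1.33 | -20.3 / -20.3 / -19.2 | 82 / 94 / 99 |
| Linear, four | 3.8 / 5.3 / 4.2 | 1.12 / 0.99 / 1.07 | -11.8 / -15.3 / -24.4 | 53 / 88 / 93 |
| Quadratic, four | 11.3 / 13.9 / 1.4 | 0.80 / 0.74 / 1.35 | -15.7 / -24.1 / -18.3 | 76 / 81 / 99 |
| Three post-baseline | 5.7 / 5.1 / 6.1 | 0.99 / 0.98 / 0.99 | -20.3 / -20.3 / -19.2 | 94 / 97 / 94 |

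Type I error and the SE ratio are from the null trials. Monte Carlo error is about 1 point near 5% or 95% and at most 2.5 points.

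**Step 5, with dropout.** A random-intercept REML fit with categorical visits and about 20% dropout (400 null trials, normal critical value) gave type I error of 11.0 / 12.8 / 12.8% with four rows and 6.5 / 7.0 / 7.5% with three.

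**Step 6, overall effect.** If the whole-study effect averages all four rows, a constant effect d becomes (0 + d + d + d)/4 = 0.75d.

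**The case against.** **The text may mean something else.** The paragraph uses baseline as a covariate and asks for post-baseline contrasts, so a programmer may well fit three rows anyway. Protocol D.6.2 names raw scores, and raw scores at four visits contain no zero row. This stands as a possible reading, but the SAP names percent change explicitly, and on the raw-score reading baseline would be both a response and a covariate. The text needs repair either way.

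**The standard-error figures describe one implementation.** The SAP does not say what drives the exponential variance. With a baseline/post indicator or the fitted mean in place of week, the likelihood had no stable optimum, and such a fit would probably fail visibly. This limits the SE figures to the week-based version.

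**The effect shape was favourable to the point.** For a gradual effect of -10/-20/-20, quadratic time gave about -11 / -19 / -20, close to the truth, though its SEs stay wrong. Protocol B.1 says interpersonal therapy, the nearest comparator, works less rapidly than CBT, so a gradual effect is plausible. On the other side, Protocol C.1.1 reports 71.9% and 87.3% binge reductions by mid-treatment. That was another trial with a different treatment, but reduction cannot exceed 100%, so a curve that falls early has to flatten.

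**Linear misfit is not due to the zeros alone.** With three rows and the gradual effect, a line still gives -13.3 / -15.5 / -21.2. This is correct, and it is why the remedy includes categorical visits. The SAP also allows higher-order terms, although only when needed.

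**It is a pilot that expects to be underpowered.** That lowers the weight of p-values, but not of the estimates and intervals that it will report.

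**Conclusion.** The concern holds. Taken literally, Primary Aim 3 puts a zero-variance baseline row into the efficacy model, and the paragraph is inconsistent about whether that row belongs there. The damage depends on how time is modelled. With categorical visits the contrasts are right, but the SE is about 30% too small at mid-treatment and about 33% too large at follow-up (ratios 0.69 and 1.33). With linear time the SEs are about right, but a nearly constant effect is understated by about 42% at mid-treatment (11.8 against 20.2) and overstated by about 26% at follow-up (24.4 against 19.4). With quadratic time both can be affected.

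The exact sizes rest on assumed SDs, correlations, visit weeks, effect shape and a week-based variance function. Percent binge reduction, the other Aim 3 outcome, was not simulated. Under no treatment effect the contrasts stay at zero, so their distortion arises only when a real effect is misfitted. The point should be fixed before analysis. It does not touch the sample size or the design.

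**What to change.** In Primary Aim 3, replace the reference to four time points with the three post-baseline assessments (mid-treatment, post-treatment, 3-month follow-up) as response rows. Keep the baseline value as a covariate, treat visit as categorical with a visit-by-arm interaction, and define the whole-study effect as the average over those three visits. Apply the same to Secondary Aim 1 if it uses change scores. The covariance structure and the therapist component can stay.

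If the sponsor prefers the raw outcomes of Protocol D.6.2, the alternative is to model all four visits with a common baseline mean across arms, categorical time and no baseline covariate.

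The cost is SAP wording and SAS code. No valid information is lost, because a participant without a post-baseline visit contributes nothing to percent change. With three visits, the random intercept and slope, AR(1) and variance function can use six parameters, as many as an unstructured 3 × 3 matrix. If that model does not converge, unstructured is the natural fallback. In the simulation it gave the same estimates and 5.0% to 6.5% null type I error.

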**D.5. Remote study procedures.** Study assessments and group therapy sessions will be conducted using an encrypted HIPAA-compliant version of Zoom videoconferencing software which we are currently using in several NIH-funded clinical trials during the stay-at-home orders. Informed consent will be collected using an electronic consent form that participants will be asked to complete during the appointment after reviewing the consent form jointly with a staff member.

**D.6. Assessments.** Assessments will be conducted by blinded assessors at baseline, mid-treatment (after session 5), post-treatment (after session 10), and at a 3-month follow-up. Our assessment strategy was specifically designed to allow for remote assessment during the COVID-19 pandemic and thus will only include measures that can be completed using videoconferencing or via the participants home computer. In order to maximize assessment completion, we will increase compensation across assessments (\$50, \$75, \$100, \$125).

**D.6.1. Feasibility and Acceptability.** Assessment of feasibility will include % of eligible patients enrolled, attrition, and study retention. We will use a Feedback Questionnaire (FQ) to obtain qualitative acceptability ratings, which will be modified from FQs used in our prior intervention development projects.

**D.6.2. Primary outcomes.** The Eating Disorder Examination is a widely utilized, semi-structured interview for the assessment of eating disorder symptoms. We will use number of binge episodes in the last 28 days and EDE global scores as the primary outcomes. Remission status will also be evaluated at each assessment following the baseline assessment and will be defined as the absence of any binge episodes or compensatory behaviors in the 28 days prior to the assessment point and an EDE global score within 1 standard deviation of the community norm (EDE global <1.74).

**D.6.3. Secondary outcomes.** We chose to use commonly-used and well-validated measures of depression (Beck Depression Inventory-II), substance use (Alcohol, Smoking, and Substance Involvement Screening Test), and quality of life (Quality of Life Inventory) to assess secondary outcome measures.

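### Aim 3 models percent change jointly at four time points although its baseline value is always zero; this can misstate visit-specific standard errors, and no fallback covariance is named

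*SAP*

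**What the plan says.** The SAP, under Primary Aim 3, names the outcomes as "percent binge frequency reduction and percent change in EDE global eating pathology". It then says "Outcomes at all four time points will be estimated jointly for maximum statistical efficiency". The covariance is built in layers. For the random part: "The model will include random effects for subject and time (with higher-order effects if needed to capture nonlinear change"). For the residual, a within-subject matrix common to both arms "with an exponential variance function to deal with heteroscedasticity and a continuous-time AR(1) correlation matrix". For clustering: "Separate variance components will be used to capture therapist and participant-within-therapist variation". The fixed effects include "baseline values of binge frequency and global eating pathology". Between-arm comparisons are covariate-adjusted contrasts at each assessment. Secondary Aim 1 reuses the same approach.

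The protocol (D.6, Assessments) schedules visits at "baseline, mid-treatment (after session 5), post-treatment (after session 10), and at a 3-month follow-up". Its section D.6.2 defines the outcomes on a different scale: "We will use number of binge episodes in the last 28 days and EDE global scores as the primary outcomes".

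The SAP does not say whether the random intercept and slope are correlated, how many therapists there are, what decides whether higher-order terms are needed in Aim 3 (AIC and BIC appear only under Aim 2), or what is done if the model does not converge.

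**The concern.** Percent change from baseline has no variance at baseline. A model with a random intercept and a positive residual variance at time 0 therefore contradicts the data there, and the baseline information is used a second time as a covariate.

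Two things follow. First, only three visits inform the within-patient covariance, while the SAP stacks three overlapping devices on it: random effects, a variance function and serial correlation. Second, if the zero rows are entered as the text says, they pull the fitted variance at early times towards zero and distort it at the later visits.

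The visit-specific contrasts and their precision are at stake. The SAP's power section expects the trial to be underpowered for formal tests and says it will rely on effect sizes, so the width of the intervals around them is central.

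**Working it through.** **The plan's own mixed-model figure.** The only one stated is N = 154 for 80% power at a medium effect (taken as d = 0.5), four assessments, alpha 0.05 (taken as two-sided) and a variance ratio of 1. With M = 4 equally spaced occasions and residual variance 1, the sampling variance of a slope is 12/((M−1)M(M+1)) = 12/60 = 0.20. Adding a slope variance of 1 gives SD = √1.2. Then n per arm = 2 × (1.96 + 0.84)² × 1.2/0.25 ≈ 75.3, so 76. The noncentral F version gives power 0.798 at N = 152 and 0.804 at N = 154, so 154 is reproduced. That calculation assumes four informative occasions and uses only a slope variance and a residual variance. It says nothing about the Aim 3 covariance model.

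**Counting.** T varying visits give T(T+1)/2 distinct variances and covariances: 3×4/2 = 6 for percent change, 4×5/2 = 10 for raw scores. The residual part has 3 parameters (variance, exponential parameter, AR(1) parameter). Ranks come from the numerical derivative of the implied covariance matrix, with visits assumed at weeks 0, 5, 10 and 23 (weekly sessions).

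| Random effects | Parameters | Rank, 3 visits (6 moments) | Rank, 4 visits (10 moments) |
|---|---|---|---|
| Linear, uncorrelated | 2+3 = 5 | 5 | 5 |
| Linear, correlated | 3+3 = 6 | 6 (saturated) | 6 |
| Quadratic, uncorrelated | 3+3 = 6 | 6 (saturated) | 6 |
| Quadratic, correlated | 6+3 = 9 | 6 (not identified) | 9 |

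The therapist variance is identified from covariances between patients of the same therapist, so it uses none of these moments.

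**How well the components are determined (three visits, assumed parameter values).** For the correlated linear model at n = 60, the expected-information SE is about 3.0 for an intercept variance of 1.0, 2.3 for a residual variance of 1.0, and 0.81 for an AR(1) parameter of 0.4. In 120 simulated trials, 76% of fits at n = 60 ended on a boundary, and 80% at n = 45 (75% of 60, the retention benchmark). With uncorrelated effects the shares were 33% and 41%. A separate REML simulation (n = 60, 80 replicates, other assumed covariances) gave 81% to 94%.

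**Effect of entering the zero baseline rows.** The model's variance at time t is g00 + 2t·g01 + t²·g11 + σ²·exp(2δt). At t = 0 this is g00 + σ², which the data force towards zero; g01 then goes towards zero as well. What remains, t²·g11 + σ²·exp(2δt), must fit all later visits and tends to climb with time. If the true SDs are flat, the compromise is too low early and too high late. The same REML simulation with equal SDs showed this:

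- Mid-treatment: mean SE 0.075 against a true 0.103. 1 − 0.075/0.103 = 0.27, so about 27% too small (28% is within the rounding), and interval coverage was 84%.
- 3 months: mean SE 0.132 against 0.103. 0.132/0.103 = 1.28, so 28% too large.

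With 30 per arm and no dropout, a true SE of 0.103 corresponds to an SD of 0.103/√(2/30) ≈ 0.40 at each visit.

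**Effect of an unplanned simplification.** Suppose the SDs are 25, 35 and 50 percentage points at the three visits (assumed), with 30 per arm. The visit-specific SEs are SD × √(2/30): 6.5, 9.0 and 12.9. A fallback with one common variance has pooled SD √((625 + 1225 + 2500)/3) ≈ 38.1, so SE ≈ 9.8 at every visit. That is 24% too small at 3 months and about 50% too large at mid-treatment. If the SDs are equal, the choice barely matters (SEs of 8.8 to 9.5 across the structures tried).

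**The case against.** A reader might infer from the counts that the Aim 3 model cannot be fitted. The documents do not support that. The SAP never says the random effects are correlated; uncorrelated linear effects need 5 parameters against 6 moments, and correlated ones are saturated but of full rank. Only the correlated quadratic version on three visits is unidentified, and higher-order terms are conditional. Saturation is not a fault in itself: the unstructured 3×3 matrix recommended below also has 6 parameters.

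The strongest counter-argument is that Aim 3 reports contrasts, not variance components, and contrasts depend on the total covariance, which can be well estimated when its decomposition is not. This was tested with 60 patients, three post-baseline visits, categorical visit means and 10% to 20% dropout (12 replicates). The 9-parameter model gave the same contrasts as the unstructured model to within 2×10⁻⁷, with identical SEs. The 6-parameter model gave SE ratios of 0.89 to 1.07. So with post-baseline visits only, boundary fits do little harm to the contrasts, and this part of the objection stands.

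It does not cover the constant baseline rows, which the text on four time points, read literally, puts into the model.

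One can also argue that raw scores were intended, as in the protocol. On four raw time points every version is identified, although the uncorrelated linear model still ended on a boundary in 21% (n = 60) and 26% (n = 45) of simulated fits. But the SAP's Aim 3 names percent change, so the conflict of scale has to be settled first.

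**Conclusion.** The point holds in limited form and is worth correcting before analysis. On the percent-change outcome, three visits supply 6 variances and covariances. The linear model uses 5 or 6 of them and is identified, though the correlated form usually ends on a boundary at n = 60. The correlated quadratic option needs 9 and is not identified. These counts follow from the SAP's text; the number for each version depends only on the unstated correlation of the random effects.

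The material risk is the literal four-row fit, with SEs misstated by roughly a quarter in opposite directions at mid-treatment and 3 months. That size rests on assumed equal SDs, assumed visit weeks and a small simulation; another variance pattern would give other errors. With post-baseline visits only, the contrasts are largely sound. What remains is unreliable variance components and no stated rule for simplifying the model.

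A reader might also infer that the model will be simplified once arm-level results are known. The documents show only that no rule is written down to prevent it.

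**What to change.** State the outcome scale for Aim 3, reconciling the protocol's raw binge count and EDE global score with the SAP's percent change. Use baseline only as a covariate, not also as a response.

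For a change outcome, fit the three post-baseline visits with:

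- fixed effects for categorical visit, arm, visit-by-arm and baseline-by-visit, alongside the planned demographic covariates;
- one unstructured 3×3 within-patient covariance in place of the random subject and time effects, the AR(1) matrix and the variance function;
- the therapist random effect, as planned;
- Kenward-Roger degrees of freedom;
- one fallback named in advance for non-convergence: heterogeneous compound symmetry, which keeps a separate variance at each visit.

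Apply the same specification to Secondary Aim 1, which inherits the Aim 3 model.

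The cost is SAP wording and simpler code, with no new data. The downside is that no smooth time trend is estimated, but the planned visit contrasts do not need one.

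### The Aim 3 fixed-effects list has a time-by-treatment interaction but no fixed effect of time, so the interaction does not test an arm difference, and the visit contrasts are sound only under a coding the SAP does not state

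*SAP*

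**What the plan says.** The Primary Aim 3 paragraph of the SAP (Statistical Design and Power) gives the fixed part of the primary efficacy model as "fixed effects for treatment arm, time by treatment interaction, demographic information, and baseline values of binge frequency and global eating pathology". Time on its own is placed in the random part: "The model will include random effects for subject and time (with higher-order effects if needed to capture nonlinear change". The outcomes are "percent binge frequency reduction and percent change in EDE global eating pathology", and the paragraph adds "Outcomes at all four time points will be estimated jointly for maximum statistical efficiency".

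The arms are to be compared "across the study as a whole, and at each assessment post-baseline", and the paragraph ends: "Time-specific covariate-adjusted contrasts will be used to compare outcome between groups". It does not name the interaction coefficient as the Aim 3 test. The software is PROC MIXED. Whether arm and time enter as CLASS factors or as numeric variables is not stated.

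Secondary Aim 1 inherits the model: "We will use the same analytic approach described above for Primary Aim 3" for depression, substance use and quality of life.

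**The concern.** A random time effect lets each participant depart from the average trend; it does not supply the trend. If no fixed time term is fitted, the mean change common to both arms must go into the terms that remain, and the only remaining fixed term involving time is the interaction with arm.

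Common change is to be expected. The SAP's power section calls supportive therapy an active condition and expects smaller effects than against a wait list. If a baseline row is kept among the four time points, percent change is zero there for everyone, so the shared trend could be large.

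The protocol (A.6, A.7) wants preliminary efficacy estimates to help decide whether a fully powered trial is worthwhile. Reading effect sizes instead of p-values, as the power section proposes, gives no protection where the estimate itself is biased.

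**Working it through.** **The plan's own figure.** The only sample-size figure for the mixed models is 154 in total. Take the linear-change power formula with four assessments, so V = 1/5, a variance ratio of 1, and 0.5 assumed for a medium effect. The noncentrality is N × 0.5² / (4 × 1.2), with an F test on 1 and N − 2 df. The smallest even N with 80% power is 154 (power 0.804), so the figure reproduces. The point below does not alter it.

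**What the listed model fits.** Suppose the arms do not differ and both improve linearly by c from first to last modelled visit. Count improvement as positive.

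1. *Arm numeric 0/1, linear time, no time term.* The supportive-therapy mean is a constant, while RRT has its own intercept and slope. The interaction therefore estimates RRT's slope, which is the whole shared slope; the true difference is 0.
2. *Arm as CLASS, linear time, no time term.* Each arm has its own slope. The default arm-by-time test has 2 df and asks whether both slopes are zero. Explicit between-arm contrasts equal those from the model with time.
3. *Arm and time both CLASS.* The design has rank 8 with or without the time main effect. Cell means and between-arm contrasts are unchanged; only the default interaction test changes meaning.

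**Size of the false contrast in case 1.** Let f be the fraction of c reached at each visit and w the generalised-least-squares weights for a constant mean. The supportive-therapy line sits at c × Σwf, so the false contrast at a visit is c × (f − Σwf).

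Assumptions not in the documents: visits at weeks 5, 10 and 23 (weekly sessions, three months taken as 13 weeks), unit variance, correlation 0.6, 30 per arm.

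- f = 0, 5/18 = 0.278, 1. Equal weights give Σwf = 1.278/3 = 0.426.
- False contrasts: −0.426c, −0.148c and +0.574c. At follow-up, c = 0.5 SD gives 0.574 × 0.5 = 0.287 SD.
- Variance of the supportive-therapy constant: (0.6 + 0.4/3)/30 = 0.0244.
- Variance of the RRT line at week 23: leverage = 1/3 + 10.33²/172.67 = 0.952, so (0.6 + 0.4 × 0.952)/30 = 0.0327.
- SE = √(0.0244 + 0.0327) = 0.239, and 0.287/0.239 = 1.20. False rejection at two-sided 5% is about 22%.
- For c = 0.15 and 0.30 SD the contrasts are 0.09 and 0.17 SD, and rejection is about 6-7% and 11%.
- With time in the model the contrast is 0 and its SE is √(2 × 0.0327) = 0.256.

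With a week-0 row added, Σwf = (0 + 5/23 + 10/23 + 1)/4 = 0.413, so the fraction is 0.587.

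**Sensitivity to covariance.** Adding a random slope (variance 0.05 per 10 weeks) to the three-visit case moves the weights to 0.433, 0.368 and 0.199. Then Σwf = 0.368 × 0.278 + 0.199 = 0.301, and the fraction is 0.70. Across the main covariance assumptions the range is about 57-71%, or 0.29-0.36 SD and 22-29% false rejection for c = 0.5 SD. Stronger random slopes push the fraction towards 80%.

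**Simulation check.** N = 60, visits at weeks 0, 5, 10 and 23, no arm difference, 400 runs. Assumed: intercept variance 0.5, slope variance 0.1 per 10 weeks, residual SD 0.6. Shared slopes of −0.2 and −0.4 per 10 weeks amount to 0.46 and 0.92 outcome units over 23 weeks.

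| Model and test | Rejection, slope −0.2 | Rejection, slope −0.4 |
|---|---|---|
| 0/1, no time: interaction | 60% | 98% |
| 0/1, no time: last-visit contrast | 28% | 71% |
| CLASS, no time: default 2-df test | 82% | 100% |
| CLASS, no time: last-visit contrast | 4% | 7% |
| Time included: interaction | 2% | 7% |
| Time included: last-visit contrast | 4% | 7% |

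The mean 0/1 interaction estimates were −0.20 and −0.40, equal to the shared slopes even though random slopes were fitted. With no shared change, every test was near 5%. Simulation error is about 1 point near 5% and 2.5 points mid-range.

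**The case against.** The strongest reply is that Aim 3 does not plan to use the damaged test. Its comparison is the set of time-specific contrasts; the interaction is a named test only in Primary Aim 2, where intercept and slope are modelled as outcomes and an average slope is implied. If arm is a CLASS factor, the Aim 3 contrasts are exactly those of the full model. This stands. A reader might infer that the plan will report shared improvement as a treatment effect, at the 60-100% rejection rates shown for the interaction. The documents do not support that: those rates belong to a test that Aim 3 does not name, and the coding that would bias the contrasts is not specified.

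The second reply is that the list is shorthand. Its random part names only subject and time, although the same paragraph earlier specifies therapist and participant-within-therapist components, so the sentence is not exhaustive. This is plausible, and a fixed time effect may well be intended, but neither document says so. The list is the only statement of the fixed effects for the primary efficacy model.

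Third, the size rests on assumed visit weeks, shared change and covariance. That is true, and small shared changes do little to the contrasts. In the equal-correlation case the three false contrasts also sum to zero, so an equally weighted whole-study comparison would not be biased; the distortion is in the pattern over visits.

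**Conclusion.** The omission is in the text, and it matters conditionally. Without a fixed time effect, the interaction is not a test of arm difference under either coding of arm. The planned visit contrasts are valid if arm is a CLASS factor. If arm is 0/1 and time linear, the follow-up contrast falsely credits RRT with roughly 57-71% of the improvement common to both arms: about 0.29-0.36 SD and 22-29% false rejection for a shared 0.5 SD.

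Those figures assume visits at weeks 5, 10 and 23 (or 0, 5, 10 and 23), linear shared change and the covariances above. The direction under 0/1 coding, the meaning of the interaction tests and the rank result do not depend on the assumed size of the shared change or on the covariance. It would go too far to say that the Aim 3 comparison is invalid as planned; its validity depends on a coding choice that the SAP leaves open.

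**What to change.** In Primary Aim 3, change the list to: *fixed effects for time, arm, the time-by-arm interaction, demographics and the baseline values*. Enter any higher-order time terms as fixed effects too, and in the interaction with arm. Categorical visit is an acceptable alternative but is not needed to cure the omission. State that inference rests on the between-arm contrasts at each visit, and say how arm and time are coded. Make the same change for Secondary Aim 1.

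The cost is one or a few extra parameters, depending on how time is coded, and a slightly larger standard error than the 0/1 model without time (0.256 against 0.239 in the example). If a fixed time effect was always intended, the edit leaves the analysis as it is.
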